- a Pre-screening Informed Consent will be signed by the participant for the use of CEACAM5 assay results on archival tumor tissue (central assessment by IHC) obtained in study EFC15858 and who had negative or moderate expression status. Participants who were pre-screened in study EFC15858 using a fresh biopsy cannot be pre-screened in Study ACT17241 unless the fresh specimen is older than 6 months at the time of pre-screening. Circulating CEA will be assessed at the pre-screening visit no more than 42 days prior to initiation of therapy.
- b Informed consent should be signed before any study specific procedures. Only participants with high circulating CEA (≥100 ng/mL) at pre-screening will be screened and will go through protocol screening procedures. Informed consent can be signed more than 28 days prior to initiation of therapy. Screening time indicates in which timeframe exams used to support eligibility have to be done prior to initiation of therapy. Routine baseline tests performed prior to ICF signature do not need to be repeated as long as they are within the screening-defined timeframe. Assessments must be performed prior to first IMP administration. Baseline evaluation should be completed within 1 week prior to initiation of therapy, except for tumor assessment, assessment of ocular/visual symptoms, and specific ocular tests that may be performed within 4 weeks prior to the first IMP administration. Results of these tests should be reviewed by the Investigator prior to initiation of therapy.
- c D1 of each subsequent cycle corresponds to D15 of the previous cycle (±2 days). Procedures can be done on the day of infusion (before infusion) or the day before.

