- d All participants should attend an on-site follow-up visit 90 days (±7 days) after the last IMP administration. SAEs/AESIs (regardless of relationship with study treatment) and IMP-related AEs ongoing at the end of study treatment, and any new IMP-related AEs/SAEs/AESIs will be followed until resolution or stabilization (stabilization is defined as an event ongoing without any change for at least 3 months). If ongoing IMP-related AEs/SAEs/AESIs are resolved or stabilized, no further safety follow-up visit is needed. If IMP related AEs/SAEs/AESIs ongoing, an on-site follow up visit will be performed every 12 weeks (±7 days). Participants who stopped treatment before documented progressive disease should undergo a tumor assessment and an on-site follow-up visit every 12 weeks (±7 days) until radiological disease progression, the start of new anti-cancer therapy, withdrawal of participant's consent, or cut-off date for secondary efficacy endpoints, whichever comes first. After documented progressive disease or the start of a new anti-cancer therapy, participants will be followed until any ongoing IMP related AEs/SAEs/AESIs are resolved or stabilized. Further anticancer treatment will be collected, including date of progression if any.

- e Circulating CEA: As per local laboratory, at pre-screening (no more than 42 days prior to initiation of therapy); at screening (within 7 days prior to initiation of therapy), then during treatment every 8 weeks, at EOT and at the follow-up visit. At screening and first tumor assessment, an additional sample for circulating CEA is requested for central assessment.
- f A fresh tumor biopsy at screening (optional) could be proposed for CEACAM5 expression assessment by IHC (retrospective, results not needed for screening and IMP treatment), WES and RNA sequencing.: Block (preferred option) or 5 slides at 5 µm thickness for IHC and 3 slides at 10 µm thickness (or equivalent quantity) for DNA/RNA evaluation are requested.
- g Plasma for Circulating CEACAM5 (central assessment) at screening within 7 days prior to initiation of therapy (the same day and time as sample for local circulating CEA assessment) and at first tumor assessment (the same day and time as sample for local circulating CEA assessment).
- *h* Includes histologic types, stage at diagnosis, disease extent at study entry.
- *i* Smoking history, tumor mutation status and PD-L1 expression.

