4 STUDY DESIGN

4.1 OVERALL DESIGN

This is a single group, Phase 2, open-label, multi-center study assessing efficacy (anti-tumor activity), safety, and PK of tusamitamab ravtansine single agent in NSQ NSCLC participants with negative or moderate CEACAM5 expression tumors and high circulating CEA (\geq 100 ng/mL) at baseline.

Moderate CEACAM5 expression is defined as intensity $\geq 2+$ in $\geq 1\%$ and <50% of tumor cells.

Negative CEACAM5 expression is defined as intensity 1+ whatever the percentage of stained tumor cells or <1% of tumor cells.

During the pre-screening phase, participants who were pre-screen failed in the EFC15858 Phase 3 trial with available CEACAM5 status (central assessment by IHC) as negative or moderate expression on archival tumor tissue can be pre-screened. Participants with high circulating CEA (\geq 100 ng/mL) will be screened and will go through protocol screening procedures.

After being screened, the eligible participants will receive tusamitamab ravtansine as a single agent treatment at the dose of 100 mg/m² Q2W until disease progression, unacceptable AE, initiation of a new anticancer therapy, or the participant's or Investigator's decision to stop the treatment, whichever comes first. A total of approximately 38 participants are planned to be treated. An interim analysis is planned after 20 participants treated are evaluable for anti-tumor activity or efficacy. If at least 2 confirmed objective responses are reported, the recruitment will continue to achieve a total of 38 evaluable treated participants.

The duration of the study for a participant will include:

- Pre-screening period: a pre-screening informed consent will be signed in order to collect available CEACAM5 expression results on archival tumor tissue from EFC15858 study and the circulating CEA value.
- Screening period: up to 28 days.
- Treatment period: once successfully screened, enrolled participants may receive study intervention until disease progression, unacceptable AE, initiation of a new anticancer therapy, or the participant's or Investigator's decision to stop the treatment, whichever comes first. Each cycle of treatment will have a duration of 2 weeks. After discontinuing study intervention, participants will return to the study site approximately 30 days after the last IMP administration or before the participant receives another anticancer therapy, whichever is earlier, for end-of-treatment (EOT) assessments.

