5.1 INCLUSION CRITERIA

Participants are eligible to be included in the study only if all of the following criteria apply:

Age

I 01. Participant must be ≥ 18 years of age (or the legal age of consent in the jurisdiction in which the study is taking place), at the time of signing the informed consent.

Type of participant and disease characteristics

- I 02. Histologically or cytologically proven diagnosis of NSQ NSCLC metastatic disease at study entry.
- I 03. Documented disease progression after at least 1 prior first chemotherapy line that must contain platinum-based chemotherapy (at least 2 cycles) and an immune checkpoint inhibitor (ICI, can be given as combined with chemotherapy or sequential, whatever the order) but no more than 2 prior chemotherapies lines are allowed. Maintenance therapy following platinum-based chemotherapy is not considered as a separate regimen. Adjuvant/neoadjuvant treatment for a participant who had a relapse with metastatic disease during or within 6 months of completion of treatment will be considered as first chemotherapy line treatment.
- I 04. For a tumor genotype with a sensitizing EGFR mutation or BRAF mutation or ALK/ROS alteration, demonstrated disease progression while receiving approved treatment for that genotype in addition to platinum-based chemotherapy and ICI.
- I 05. Moderate or negative CEACAM5 expression assessed by a central IHC assay in an archival tumor sample. Moderate CEACAM5 expression is defined as intensity ≥2+ in ≥1% and <50% of tumor cells. Negative CEACAM5 expression is defined as intensity 1+ whatever the percentage of stained tumor cells or <1% of tumor cells.

- I 06. Circulating CEA levels ≥ 100 ng/mL at pre-screening.
- I 07. Measurable disease by RECIST v1.1 (Section 10.12), as determined by the Investigator. At least 1 measurable lesion is required. A previously irradiated tumor lesion is considered measurable if progression has been demonstrated in the lesion. The lesion must be ≥10 mm in the longest diameter (except lymph nodes, which must have a short axis ≥15 mm) as imaged in computed tomography (CT; preferred) or magnetic resonance imaging (MRI) scans.

I 08. Eastern Cooperative Oncology Group (ECOG) performance status 0-1.

Weight

Not Applicable.

Sex, contraceptive/barrier method and pregnancy testing requirements

I 09. All participants (male and female)

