1.1 STUDY DESIGN

This is a single group, Phase 2, open-label, multi-center study assessing efficacy (anti-tumor activity), safety, and PK of tusamitamab ravtansine single agent in NSQ NSCLC participants with negative (ie, intensity 1+ whatever the percentage of stained tumor cells or <1% of tumor cells) or moderate (ie, intensity \geq 2+ in \geq 1% and <50% of tumor cells) CEACAM5 expression tumors and high circulating CEA (\geq 100 ng/mL) at baseline.

During the pre-screening phase, participants who were pre-screened failed in the EFC15858 Phase 3 trial with available CEACAM5 status (central assessment by immunohistochemistry, IHC) as negative or moderate expression on archival tumor tissue can be pre-screened for ACT17241 study. Participants with high circulating CEA (≥100 ng/mL) will be screened and will go through protocol screening procedures.

This study is designed to obtain preliminary efficacy, safety and PK data on tusamitamab ravtansine administered as monotherapy at 100 mg/m² Q2W to participants with NSQ NSCLC tumors with CEACAM5 moderate-negative tumor expression and high circulating CEA levels.

Approximately 285 participants will be pre-screened to achieve approximately 38 treated participants, based on an estimated pre-screening failure rate of 84% and an estimated study screening failure rate of 15%.

The cycle duration is 2 weeks. The median expected duration of study per participant is estimated as 40 weeks: up to 4 weeks for screening, a median of 24 weeks for treatment, and a median of 12 weeks for end of treatment assessments and the safety follow-up visit. Enrolled participants may receive study intervention until disease progression, unacceptable AE, initiation of a new anticancer therapy, or the participant's or Investigator's decision to stop the treatment, whichever comes first.

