3.7.2 Biomarker analyses

Several exploratory objectives related to pharmacodynamic/genomic endpoints will be considered in this study.

Unless otherwise specified, biomarkers analyses will be performed on participants with available data from the all-treated population.

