3.7.2.1.1 Circulating CEA levels before IMP and CEACAM5 IHC

Circulating CEA levels before IMP will be correlated with IHC CEACAM5 expression status (for prescreened participants). To this end, the closest circulating CEA assessment to biopsy (or the oldest value before IMP if the date of the biopsy is missing) will be considered. The circulating CEA levels (quantitative) will be presented using descriptive statistics, according to IHC CEACAM5 expression status (negative vs. moderate expressers; or according to the % of tumoral cells expressing CEACAM5 at intensity $\geq 2+$). The association between the circulating CEA levels (quantitative) and the CEACAM5 expression will be also assessed and visualized graphically. The time from tumor biopsy collection and circulating CEA assessment (the closest to biopsy) will be also described and investigated in the correlation between circulating CEA levels and IHC CEACAM5 expression.

In order to evaluate the variability of circulating CEA values, an intraclass correlation coefficient will be calculated between pre-screening and screening circulating CEA values (when both available). A graphical visualization may be provided to observe the degree of concordance. Similarly, the concordance between the circulating CEA and the circulating CEACAM5 will be evaluated.

3.7.2.1.2 Modulations of circulating CEA as a potential PD biomarker of response to tusamitamab ravtansine treatment

The circulating CEA at different timepoints and its relative change from baseline will be presented using descriptive statistics by response status and overall. Depending on the data available, some timepoints may not be presented when the sample size is too small.

A graphical visualization (spaghetti plot) will be presented to visualize the relative change from baseline of circulating CEA values for each participant, annotated with the best overall response.

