4 SAMPLE SIZE DETERMINATION

Assuming a pre-screening failure rate of 84% and a study screening failure rate of 15%, approximately 285 participants will be pre-screened to achieve approximately 38 treated participants in the study.

The initial plan is to treat a total of 38 participants evaluable for anti-tumor activity (at least 1 postbaseline tumor assessment, early clinical progression, or death due to disease progression).

Estimated ORR and 95% exact CIs by number of responders from a sample size of 38 evaluable participants for anti-tumor activity are listed in Table 7.

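### The planned ICC for CEA variability uses only pairs whose first value was at least 100 ng/mL, so it will usually understate repeatability in the pre-screened population; label it and lead with within-participant variation on the log scale

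*SAP*

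**What the plan says.** SAP 3.7.2.1.1 sets out to describe the variability of circulating CEA before treatment: "an intraclass correlation coefficient will be calculated between pre-screening and screening circulating CEA values (when both available". A concordance plot is optional. The form of the ICC is not given. SAP 3.7.2.1 treats CEA as quantitative and mentions no log transformation.

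Who can supply a pair is fixed by the protocol. Inclusion criterion I 06 requires "Circulating CEA levels ≥ 100 ng/mL at pre-screening". Note b to the study flow chart (Protocol 1.3.1) adds: "Only participants with high circulating CEA (≥100 ng/mL) at pre-screening will be screened and will go through protocol screening procedures". Note e places the second sample "at screening (within 7 days prior to initiation of therapy), then during treatment every 8 weeks". No eligibility criterion applies to that second value.

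By default, under SAP 3.7.2, "biomarkers analyses will be performed on participants with available data from the all-treated population". SAP section 4 sizes the funnel as follows: "Assuming a pre-screening failure rate of 84% and a study screening failure rate of 15" per cent, approximately 285 are pre-screened to treat approximately 38.

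**The concern.** An ICC is the between-participant variance as a share of the total. It therefore depends on how widely the sampled participants differ, as well as on how well the measurement repeats. Keeping only participants whose first value passed a high cut-off removes much of the between-participant spread and leaves the within-participant noise in place. It also brings in regression to the mean, because some first values passed the cut-off through upward error.

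Neither document mentions range restriction, a correction, or a conditional label. Nor does either plan a within-participant SD or CV, which would show variability without depending on spread. The trial enters participants on one CEA value that may be up to 42 days old. An unlabelled, moderate ICC could be read as showing that CEA is an unstable marker when the low figure comes largely from the entry cut-off.

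**Working it through.** **1. The plan's own figure.** 38 / (0.16 × 0.85) = 279.4. Rounding up at each stage, 38 / 0.85 gives 45 and 45 / 0.16 gives 282. Forward, 285 × 0.16 = 45.6 screened, and 45.6 × 0.85 = 38.8 treated. The stated 285 is consistent with this. About 38 pairs are expected in the all-treated population, or about 45 among all screened.

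**2. Share below the cut-off.** Protocol 4.1 says that the pre-screening consent serves to collect CEACAM5 results from the "EFC15858 study and the circulating CEA value". CEACAM5 status is already known, so CEA is the new information at this step and 84% is a reasonable proxy for the share below 100 ng/mL. It is an upper bound, because SAP Appendix 2 counts anyone not subsequently screened as a pre-screen failure, whatever the reason.

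**3. Model (assumed, not in the documents).** Log CEA is bivariate normal with unit variance at both times and correlation ρ, which is the true ICC. Pairs are kept if the first value exceeds the quantile q, with c = Φ⁻¹(q) and λ = φ(c)/(1 − q). Then:

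- variance of the first value: v₁ = 1 − λ(λ − c)
- variance of the second value: v₂ = ρ²v₁ + 1 − ρ²
- covariance: k = ρv₁
- mean shift between the two values: d = λ(1 − ρ)
- consistency ICC = 2k/(v₁ + v₂)
- agreement ICC = k/[(v₁ + v₂)/2 + d²/2]
- one-way ICC = (k − d²/4)/[(v₁ + v₂)/2 + d²/4]

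**4. Numbers for q = 0.84, ρ = 0.90.** c = 0.9945, λ = 1.521, v₁ = 0.200, v₂ = 0.352, k = 0.180, d = 0.152. The pre-screening variance falls to 20% of its full value. The consistency ICC is 0.65, the agreement ICC 0.63 and the one-way ICC 0.62. In samples of 38 pairs the median agreement ICC is 0.61 (95% of samples 0.37 to 0.78).

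**5. Sensitivity (one-way ICC, normal log CEA).**

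| Share below 100 ng/mL | True 0.80 | True 0.90 | True 0.95 |
|---|---|---|---|
| 50% | 0.59 | 0.77 | 0.87 |
| 60% | 0.54 | 0.73 | 0.86 |
| 75% | 0.45 | 0.67 | 0.82 |
| 84% | 0.37 | 0.62 | 0.78 |

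If the underlying log CEA is instead exponential, hence strongly right-skewed, a true 0.90 reads about 0.89 in the top 16%.

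**6. Raw scale.** Take log-scale reliability 0.90, 38 pairs and log-SD 1.0, 1.5 or 2.0. The median raw ICC is 0.68, 0.65 or 0.60 with selection, against 0.84, 0.78 or 0.70 without it. Selection costs about 0.10 to 0.17; the rest of the shortfall from 0.90 is the effect of skewness. If the raw ICC itself is 0.90 and log-SD is 0.5, 1.0 or 1.5, the selected pairs read about 0.72, 0.81 or 0.87.

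**7. Within-participant SD.** From half the mean squared difference it is √{[(1 − ρ)²(1 + cλ) + 1 − ρ²]/2}. At q = 0.84 and ρ = 0.90 this is √{[0.01 × 2.512 + 0.19]/2} = 0.328. Without selection it is √(1 − ρ) = √0.10 = 0.316. Truncation that lowers the ICC from 0.90 to 0.62 moves this measure by about 4%.

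**8. Crossing the cut-off.** Under the same model about 27% of pairs would have a screening value below 100 ng/mL.

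**The case against.** An ICC always belongs to a population. For participants selected at 100 ng/mL or more, the complete-pair ICC is a correct description. The default biomarker population is exactly such a group, and the ICC sentence names no wider one. This stands: the statistic is biased only if it is read as describing CEA in the pre-screened population. The SAP does not say which is meant, and the preceding paragraph of the same section works with prescreened participants, so the wider reading is easy to make.

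The size is uncertain. No document gives the distribution of CEA, the analysis scale, the true ICC or the share failing on CEA alone. This also stands. A reader might infer that 0.90 will read as 0.6, but that is near the severe end of the range.

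A reader might also infer that this ICC is the trial's test of whether CEA is stable enough to select on, or to stand in for tissue expression. The SAP states only a descriptive aim and attaches no threshold or decision to it.

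Crossing below 100 ng/mL will be partly visible already. Baseline is the last value before dosing (SAP 3.1), and the subgroups in SAP 3.7.3 include baseline CEA below 100 µg/L. That covers treated participants but not those who fail screening.

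Finally, a likelihood-based ICC using all pre-screening values is tempting as a replacement. Under normality it recovers a median of 0.90 (5th to 95th percentile 0.80 to 0.93) when the truth is 0.90. However, it extends a relation seen in the top 16% to participants with no second value. In an assumed case with noisier measurement at low CEA and a full-population ICC of 0.77, it reads 0.83. It does not justify dropping the direct statistic.

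**Conclusion.** The concern holds in limited form. Every pair is truncated on its first value by the entry rule, and nothing in the plan labels or offsets this. The ICC will therefore usually understate CEA repeatability in the pre-screened population. A true 0.90 would read about 0.62 with normal log CEA and all 84% failing on CEA, about 0.77 with half below the cut-off, and up to about 0.89 with strongly right-skewed log CEA. The truncation follows from the documents; the true ICC, the distribution and the share failing on CEA are assumptions.

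The documents do not support reading this as a flaw in eligibility or in the efficacy conclusions. The analysis is exploratory and leaves the ORR and the interim rule untouched. It still merits a change, because as written the statistic can mislead for its stated purpose and the correction is cheap.

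**What to change.** In SAP 3.7.2.1.1:

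1. Label the complete-pair ICC as conditional on pre-screening CEA of at least 100 ng/mL, compute it on log CEA and state its form.
2. Make the within-participant SD or CV on the log scale, with limits of agreement, the main variability measure. Note that part of any mean fall from pre-screening to screening is regression to the mean.
3. Report the percentage of screened participants whose screening CEA is below 100 ng/mL.
4. Optionally, add as a sensitivity analysis a likelihood-based ICC on log CEA that uses the pre-screening value of all pre-screened participants. State that it relies on log-normality and on constant error variance below the cut-off.

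The cost is a few lines of SAP text and a little more analysis work. No new data are needed.

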3.7.2.2 Circulating free DNA (cfDNA)

3.7.2.2.1 Relationship between the tumor mutation profiles detected in the circulating free DNA (cfDNA) at baseline with efficacy outcomes

Genomic alterations collected locally from the eCRF at pre-screening will be described. For each gene, participants will be grouped into two groups: "altered" (ie, participants with at least one alteration for the gene) and "wild-type" (ie, participants without alteration for the gene) and described using descriptive statistics by IHC CEACAM5 expression status and overall. The confirmed objective response rate and two-sided 95% confidence intervals using the Clopper-Pearson method will be presented for each gene in the all-treated population.

Circulating-free DNA (cfDNA) centrally assessed will be collected and analyzed in the same way as local data from eCRF.

3.7.2.3 To explore potential sets of biomarkers from tumor DNA and RNA analyses as potential biomarkers of response to tusamitamab ravtansine

The same tumor biopsy as the one sent for CEACAM5 assessment at pre-screening may be used for additional tumor DNA and/or RNA analyses, if enough relevant data is collected.

Additional exploratory analyses on biomarkers from tumor DNA and RNA analyses, beside target expression, as potential biomarkers of response to tusamitamab ravtansine might be conducted..

3.7.3 Subgroup analyses

Subgroup analyses of the primary efficacy endpoint (defined in Section 3.2.1) will be performed to assess the homogeneity of the treatment effect across the following subgroups (categories with fewer than 5 participants may be combined with other categories):

- Race (White, Other)
- Age group (<65, ≥ 65 years)
- Gender (Male, Female).
- ECOG PS at baseline (0,1)
- Smoking status (Never, Former and Current)

Property of the Sanofi group - strictly confidential

- Programmed death ligand-1 (PD-L1) expression (<1%, $\ge1\%$)
- Circulating CEA at baseline ($\geq 100 \ \mu g/L$),
- Circulating CEA at baseline and CEACAM5 expression (CEACAM5 1-49% and CEA <100 μ g/L, CEACAM5 1-49% and CEA \geq 100 μ g/L, CEACAM5 <1% and CEA <100 μ g/L, CEACAM5 <1% and CEA \geq 100 μ g/L)
- Prior treatment with EGFR, ALK, or ROS1 inhibitors (Yes, No)
- Time from initial diagnosis (<12 months, \geq 12 months)
- Brain metastases (Yes, No)
- Number of organs involved (including primary tumor location) ($<3, \geq 3$)

If a sufficient number of responses is observed, tables will be provided, otherwise subgroup information will be displayed in listings only. For tables, Objective response rate estimate and the corresponding 95% CI, will be provided for each subgroup, using the same method as applied to the primary analysis. Forest plots will be provided.

